6.5 BLINDING AND UNBLINDING

This study is double-blinded. Study drugs and placebo are filled in amber vials with a 1.2-mL fill volume, are clear and colorless liquids, and labeling is identical. The pharmacist and/or pharmacy technician at the clinical site will fill syringes for each study subject on dosing days to maintain the blind of the study staff. However, once a subject has been dosed with Scop HBT, Injection, the study staff will likely become unblinded as the CNS effects of Scop HBT will be evident in the participants, especially at the higher concentrations. Nevertheless, every effort should be made to maintain the blind, even at the higher concentrations.

In addition to the study pharmacist, another Pharmaron team member is unblinded in order to verify the dosing calculations at the time of subject treatment. One (1) Battelle statistician, one (1) pharmacokineticist, and PK sample analysts will be unblinded. The unblinded statistician will prepare the study data for the DSMB closed session meetings, including the PK data received from the pharmacokineticist.

Battelle will have a blinded statistician. The blinded statistician and all other Battelle staff responsible for cleaning the data and creating and validation of the tables, listings, and figures (TLFs), specifically the data management, statistics and programming staff, will be blinded throughout the study. Unblinding of the treatment levels will occur after all analysis populations are finalized and the final database is locked.

6.6 HANDLING OF MISSING VALUES, PARTICIPANT WITHDRAWAL, AND STUDY TERMINATION

Missing data can occur due to protocol deviations and withdrawal of participants from the study. All data documented in the CRFs will be presented in data listings. This means that missing values are listed as missing values. Repeated and additional measurements are listed as well.

6.6.1 Assessment of Missing

All missing datapoints will be identified from review of data listings. A table and listing of all missing data points will be generated for each endpoint with any missing. For each missing observation, the cause of missing will be identified from protocol deviations and participant disposition. Endpoints censored due to administration of rescue medication (as detailed in 6.11) will be presented separately. All protocol deviations will be listed by participant. The number of protocol deviations and the number of participants with protocol deviations will also be summarized by deviation category and by deviation classification (major/minor). If missing data is identified without a protocol-related reason or a protocol deviation, the missing measure will be added as protocol deviation.

6.6.2 Handling of Missing PK Data

For PK, a subject will be included in the calculation of the PK endpoints even if the subject has missing data at certain time points, as long as the subject has post-baseline data to define the PK plasma profile, i.e. a well-defined Cmax, Tmax, and at least three concentration time points to characterize the terminal linear phase.

Plasma concentration below the level of quantification (BLQ) will be censored. For the intended assay for Scopolamine, the limit of quantification is 0.010ng/mL. The upper limit of quantification is 10.0ng/mL. For samples that exceed the upper limit of quantification, dilution will be used to obtain quantifiable samples.

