13.1. Accounting for Missing, Unused, and Spurious Data

Instances of missing data will be reported along with a reason that data is missing. If multiple measurements are collected, a reason for repeat measurement will be recorded, and the data point corresponding to erroneous or incomplete data collection will be censored. Otherwise, all data will be included in the analysis as specified in the SAP. Data collected following administration of rescue medication will be censored in the analysis of endpoints that are likely to be affected by the rescue medications (BPRS, RASS, DSST, C-SSRS). However, injection site VAS scores will not be censored following administration of rescue medications.

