5.2.1 Plasma Pharmacokinetics

The PK parameters will not be calculated as part of this SAP, but they will undergo statistical analysis according to this SAP. The PK parameters will be calculated by the Battelle Chemistry Technical Center according to their Standard Operating Procedures and conventions, using WinNonlin Phoenix v8.1). Plasma concentration time profiles for each subject tested will be evaluated using semi-log plots and characterized using noncompartmental analysis.

Descriptive statistics for the concentration of Scopolamine in plasma and for the PK parameters will be calculated at each scheduled time point. The summary of descriptive statistics at each time point will be displayed by cohort and dose level. The statistics will include sample size, mean, median, standard deviation (SD), standard error of the mean (SEM), percent coefficient of variance (CV), minimum, and maximum for continuous variables, and 95% confidence intervals. Additionally, geometric means will be calculated for AUC_{∞} and C_{max} .

Analysis of plasma concentrations will be performed for each subject on samples collected prior to dosing and at the following post-dose target time points: 2, 5, 10, 15, 20, and 30 minutes and 1, 2, 4, 8, 12, 24, 36, and 48 hours post dose. Table 6 describes the time windows for blood draw. PK parameters will be calculated using the time points of the actual blood draw, rather than the target time. The serum PK parameters that will be analyzed are listed below and are outlined and defined as in the protocol:

- **C_{max}** : Maximum measured plasma concentration over the time span specified.
- **T_{max}** : Time of maximum measured plasma concentration. If the maximum value occurs at more than one time point, T_{max} is defined as the first time point with this value.
- **$t_{1/2}$** : Apparent first-order terminal elimination half-life will be calculated as $0.693/k_e$.
- **V_d/F** : Apparent Volume of distribution.
- **Cl/F** : Apparent Volume of blood or plasma cleared of drug per unit time.
- **MRT (Mean Residence Time)**: Mean time the drug spends in the body before being eliminated.
- **AUC_{last}** : The area under the plasma concentration versus time curve, from time 0 to the last measurable concentration, as calculated by the linear trapezoidal method.

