6.6.3 Handling of Other Missing Data

Other than AE data, for which missing will be imputed as the most severe, missing values will not be imputed for statistical summaries or analysis. All planned analyses of non-AE data will be conducted using all available data, including for participants who withdraw, with the exception of data to be censored following administration of rescue medications (as detailed in 6.11). In the event of study termination, all available data will be used for analysis of cohorts with at least one participant receiving the study drug.

Unless indicated otherwise, summary statistics will be reported for observed data only, with the exception of the cases described below.

Partial or incomplete start/end dates of the AEs or concomitant medications will be imputed to help determine treatment-emergent adverse events and prior or concomitant medications.

For incomplete start dates, following imputation rules will be implemented:

- Missing day - Impute as the 1st of the month unless month is same as month of first dose of study drug then impute using the day of first dose date.
- Missing day and month – impute as 1st January unless year is the same as first dose date then impute using the day and month of first dose date.

- Completely missing – impute using the first dose date unless the end date suggests it could have started prior to this in which case impute as 1st January of the same year as the end date.

When imputing a start date, ensure that the new imputed date is sensible i.e. is prior or equal to the end date of the AE or medication.

For incomplete end dates following imputation rules will be implemented:

- Missing day - Impute as the last day of the month unless month and year are the same as the month and year of the end of study, then impute as the end of study date.
- Missing day and month – Impute as 31st December unless year is the same as the year of the end of study date then impute as the end of study date.

Completely Missing – need to look at whether the AE/medication is still ongoing before imputing a date and also when it started in relation to study drug. If the ongoing flag is not missing then assume that AE is still present / medication is still being taken (i.e. do not impute a date). If the AE/medication has stopped and start date is prior to first dose date then impute as the 1st dose date, if it started on or after first dose date then impute as the end of study date.

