6.11 EXTENT OF EXPOSURE AND TREATMENT COMPLIANCE

This is a single dose study where the treatment is given in a single IM injection. The study medication (active or placebo) will be prepared by the pharmacist in accordance with the Drug Preparation Manual. Therefore, exposure will be closely monitored, and treatment compliance is not a major risk.

In the event that rescue medications (physostigmine, atropine, diazepam or lorazepam) are administered, data for the participant will be analyzed according to the dosage of Scop HBT received for measures taken up to the administration of the rescue medication. Thereafter, participant data will be treated differently by endpoint. Data collected after administration of the rescue medication for the BPRS, DSST, and/or RASS will be censored in analyses, though presented descriptively. Adverse events, injection site VAS, and PK data will not be censored.

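### SAP 6.6.2 does not define how concentrations below the quantification limit are handled; on its natural reading, late concentration summaries are biased upward by an amount that depends on time and dose

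*SAP*

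**What the plan says.** SAP 6.6.2, headed as a section on missing PK data, states: "Plasma concentration below the level of quantification (BLQ) will be censored". It adds that "the limit of quantification is 0.010ng/mL". It gives no substitution value, no left-censored method, no separate treatment of pre-dose, intermediate and trailing results below the limit (BLQ), and no minimum number of quantifiable values for a mean.

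SAP 5.2.1 commits to the summaries that this rule feeds: "Descriptive statistics for the concentration of Scopolamine in plasma and for the PK parameters will be calculated at each scheduled time point". They are given by cohort and dose level and include sample size, mean, median, SD, SEM, CV and 95% confidence intervals. Samples are taken pre-dose and at "2, 5, 10, 15, 20, and 30 minutes and 1, 2, 4, 8, 12, 24, 36, and 48 hours post dose".

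Three other places bear on the meaning of the rule:

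- Protocol 13.1, on repeat measurements: "the data point corresponding to erroneous or incomplete data collection will be censored".
- SAP 6.11, on certain scales after rescue medication: the data "will be censored in analyses, though presented descriptively".
- SAP 6.6.3, which bars imputation of values other than adverse event data and adds: "Unless indicated otherwise, summary statistics will be reported for observed data only".

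**The concern.** A BLQ result is not missing. It says that the concentration is low. If such results are removed, each late row of the concentration table describes only the subjects whose drug levels were still high enough to measure. The mean and median rise, and the SD, CV and confidence interval describe a truncated sample. If every subject is properly BLQ before dosing, the pre-dose row has no data at all.

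Characterising the pharmacokinetics of ascending doses is a primary objective, and SAP 6.1 says it will be addressed mainly through descriptive statistics. If the term was meant in another sense, the SAP still names no method, and two programmers could produce different tables from the same data.

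**Working it through.** **Meaning of the term.** In protocol 13.1, censoring a data point removes it. In SAP 6.11 it removes the value from analyses but leaves it in descriptive displays. SAP 6.6.3 then leaves no imputed value to put in its place. Exclusion is therefore the natural reading for BLQ results, but it remains an inference.

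**Direction of the bias.** For a lognormal concentration X with log-scale SD σ, BLQ share f and a = Φ⁻¹(f):

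E[X | X ≥ limit] / E[X] = Φ(σ − a) / (1 − f)

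This is never below 1. For σ from 0.3 to 1.3 it is 1.2 to 1.8 at 50% BLQ and 1.4 to 2.9 at 75% BLQ. Against a table that scores BLQ as zero, the inflation is exactly 1/(1 − f): 2-fold at 50% and 4-fold at 75%.

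**Size.** The documents give no BLQ shares and no bias figure, so there is none to reproduce. Inputs:

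- AUC 0.94 h·ng/mL at 0.005 mg/kg (protocol 5.2.2), scaled in proportion to dose.
- Half-life 220 min (protocol 5.2.4, a subcutaneous study), so k = 0.693/3.67 = 0.189 per hour.
- Limit 0.010 ng/mL (SAP 6.6.2).
- Assumed, not in the documents: between-subject CV of 40% or 66% on AUC and 20% on k, both lognormal.

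Model: C(t) = AUC × k × exp(−kt). For a subject at the central values on 0.021 mg/kg at 24 h, AUC = 0.94 × 4.2 = 3.948 and C = 3.948 × 0.189 × exp(−4.537) = 0.0080 ng/mL, just under the limit. On 0.005 mg/kg at 12 h, C = 0.0184 ng/mL, above it.

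A simulation of 1,000,000 subjects per case gave the following. The factor is the mean of quantifiable values divided by the true mean; ranges run over the two AUC CVs.

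| Dose (mg/kg) | 12 h factor | 24 h quantifiable | 24 h factor | Six-subject cohorts with no quantifiable value at 24 h |
|---|---|---|---|---|
| 0.005 | 1.09-1.22 | 0.5-1.4% | usually no mean | 92-97% |
| 0.007 | 1.03-1.10 | 2-4% | usually no mean | 78-87% |
| 0.011 | 1.00-1.03 | 10-12% | 2.7-3.1 | 47-52% |
| 0.014 | 1.00-1.01 | 18-19% | 2.3-2.6 | 29-30% |
| 0.021 | 1.00 | 34-37% | 1.8-2.0 | 6-9% |

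The factors apply to cohorts in which a mean can be computed. At 36 h fewer than 1% of values are quantifiable at any dose, and at least 95% of six-subject cohorts have none.

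**Sensitivity.** These cases assume CVs of 30%/20% or 50%/30% for AUC/half-life.

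- Scaling the AUC from the intravenous study in protocol 5.2.4 (6.749 × 0.35/0.7975 = 2.96 h·ng/mL at 0.005 mg/kg) and keeping the 220-minute half-life gives 15-79% BLQ at 24 h and factors of 1.1 to 2.4.
- With that AUC and an 8 h half-life, 24 h is almost clear (0-6% BLQ), and the problem moves to 48 h (26-95% BLQ, factors 1.2 to 3.1).
- If the comparator scores BLQ as half the limit, the factor stays at or below about 2.2 in every scenario.

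**Effect on PK parameters.** Cmax and Tmax come from quantifiable samples. AUClast stops at the last measurable concentration, so trailing BLQ results do not enter it. If the pre-dose BLQ value were dropped, only the area from 0 to 2 min would be in question. Even with the 2-minute sample at the projected Cmax of 0.68 ng/mL, that area is 0.5 × (2/60) × 0.68 = 0.011 h·ng/mL, about 1.2% of 0.94.

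**The case against.** The strongest reply is that no document says BLQ values are removed from the concentration table. SAP 6.11 keeps censored data in descriptive displays, and the concentration table is descriptive. The observed-data sentence in SAP 6.6.3 stands under other missing data, not PK data. This is fair, and it is why the finding is an undefined rule with a likely reading rather than a stated deletion. It does not remove the problem: a BLQ result has no numeric value to present in a mean unless one is assigned, and the SAP assigns none.

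The plan also has partial safeguards. Sample size is reported at each time point, so lost subjects would show, and protocol 12.1.1 provides individual listings. The median is reported too, but a median of quantifiable values alone is itself biased. SAP 4.3 and 6.15.1 place parameter calculation in a separate PK manual and report, which may already state a convention for noncompartmental analysis. That covers the parameters; the concentration summaries remain under this SAP.

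The absolute error is small. At 0.021 mg/kg and 24 h the quantifiable-only mean is 0.017-0.019 ng/mL against a true 0.0097. The gap is under 0.01 ng/mL, against a dose-scaled Cmax of 0.68 × 4.2 = 2.9 ng/mL. This stands, and it limits the weight of the point.

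**Conclusion.** The point holds for the descriptive concentration summaries. If BLQ values are excluded, late means, medians, SDs, CVs and confidence intervals describe quantifiable subjects only, and the pre-dose row may be empty. Under the stated inputs the mean is overstated by about 0-22% at 12 h and about 1.8- to 3-fold at 24 h for 0.011-0.021 mg/kg. These figures rest on assumed between-subject CVs, dose-proportional exposure and a single-exponential decline. A different half-life moves the affected times.

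Two stronger readings are tempting but not supported:

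- **A general 2- to 4-fold overstatement of late means.** One route to it starts the decline at the Cmax of 0.68 ng/mL with a 220-minute half-life. That implies an AUC of 0.68 × 3.67/0.693 = 3.6 h·ng/mL, against the 0.94 given in the same sentence of protocol 5.2.2. With the stated AUC the bias is slight at 12 h, and at 36 h there is usually no mean to distort.
- **Damage to half-life estimates, dose comparisons or escalation advice.** Parameters come from each subject's own profile, and no planned test compares mean concentrations. The tests use PK parameters, including Cmax/Dose and AUC∞/Dose, which dropping trailing BLQ values leaves essentially unchanged. Protocol 10 expects cohort profiles to assist the DSMB, but nothing ties them to the SAP 6.6.2 rule.

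**What to change.** In SAP 6.6.2, replace the censoring sentence with two separate rules.

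1. **Concentration summaries.** Keep every sampled subject in the denominator. Score BLQ results, pre-dose and post-dose, as zero; half the limit is an acceptable alternative if it is fixed in advance. Report the number BLQ at each time point, show the median, and do not report the mean (or the SD, SEM, CV and confidence interval that depend on it) when more than half are BLQ.
2. **Noncompartmental analysis.** Set BLQ results before the first quantifiable sample to zero and ignore those after the last one, or cross-refer to the PK manual if it already states the convention.

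The cost is SAP wording and a count of BLQ results in the table shell, with no new data. Zero substitution biases means slightly downward; the suppression rule limits this. Under the central inputs most 24 h means would be withheld, which is the honest result when most of a small cohort is below the limit.

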6.6.3 Handling of Other Missing Data

Other than AE data, for which missing will be imputed as the most severe, missing values will not be imputed for statistical summaries or analysis. All planned analyses of non-AE data will be conducted using all available data, including for participants who withdraw, with the exception of data to be censored following administration of rescue medications (as detailed in 6.11). In the event of study termination, all available data will be used for analysis of cohorts with at least one participant receiving the study drug.

Unless indicated otherwise, summary statistics will be reported for observed data only, with the exception of the cases described below.

Partial or incomplete start/end dates of the AEs or concomitant medications will be imputed to help determine treatment-emergent adverse events and prior or concomitant medications.

For incomplete start dates, following imputation rules will be implemented:

- Missing day - Impute as the 1st of the month unless month is same as month of first dose of study drug then impute using the day of first dose date.
- Missing day and month – impute as 1st January unless year is the same as first dose date then impute using the day and month of first dose date.

- Completely missing – impute using the first dose date unless the end date suggests it could have started prior to this in which case impute as 1st January of the same year as the end date.

When imputing a start date, ensure that the new imputed date is sensible i.e. is prior or equal to the end date of the AE or medication.

For incomplete end dates following imputation rules will be implemented:

- Missing day - Impute as the last day of the month unless month and year are the same as the month and year of the end of study, then impute as the end of study date.
- Missing day and month – Impute as 31st December unless year is the same as the year of the end of study date then impute as the end of study date.

Completely Missing – need to look at whether the AE/medication is still ongoing before imputing a date and also when it started in relation to study drug. If the ongoing flag is not missing then assume that AE is still present / medication is still being taken (i.e. do not impute a date). If the AE/medication has stopped and start date is prior to first dose date then impute as the 1st dose date, if it started on or after first dose date then impute as the end of study date.

For partial or completely missing datetime (s), impute 00:00 if both minutes and seconds are missing. If minutes or seconds are missing, impute 00 accordingly. Make sure the new imputed datetime are sensible and does not affect the assignment of the AEs or Concomitant medication as treatment-emergent or ongoing respectively.

6.7 INTERIM ANALYSES

No interim analyses are planned. DSMB review will review data from each cohort. Dosing or enrollment may be halted if escalation criteria are not met. The DSMB may also recommend halting the trial at any point.

6.7.1 Dose Progression Criteria

Dosing may be halted prior to study completion. The criteria that require halting enrollment are specified in [Table 3](#). Once halted the PI and DSMB will make recommendations to the sponsor on whether to resume enrollment.

6.7.2 Independent Data Safety Monitoring Board (DSMB) Analyses

An independent data safety monitoring board (DSMB) is required for this study. The DSMB will review safety and PK data for each cohort prior to cohort escalation. The DSMB will not conduct any statistical analyses or use a statistical test to determine whether to halt or terminate the trial.

6.8 ADJUSTMENT FOR MULTIPLE COMPARISONS

Section [6.3](#) specifies the hypotheses to be tested in this Phase 1 trial of the safety and pharmacokinetics of IM injection of Scop HBT. Given the large number of hypothesis tests, the Benjamini-Hochberg method will be used to determine statistical significance. As this trial is exploratory, a relatively high false discovery rate (FDR), the proportion of significant findings that are spurious, will be used. For this study, the FDR will be set at 0.20. The choice of a high FDR prevents rejecting marginally significant findings, which may provide important information about the drug's safety and pharmacokinetic properties. With 110 tests and an FDR of 0.20, the threshold for statistical significance for the five lowest p-values will be 0.0018,

0.0036, 0.0055, 0.0073, and 0.0091. Statistical significance of tests will be noted using at the alpha = 0.05 level as well as through the Benjamini-Hochberg method. Study sponsors should note that one-in-five significant findings obtained through this process are expected to be spurious.

6.9 POOLING OF SITES

Not applicable for the study since only 1 investigative site is being utilized.

6.10 DISTRIBUTIONAL ASSUMPTIONS

The residuals of ANOVA models will be assessed for normality using a Shapiro-Wilk test in conjunction with visual inspection of quantile-quantile plots. Lognormality is commonly assumed for PK parameters. If the normality assumption is not met, logarithmic (natural or base-10) transformation will be assessed. If lognormality is rejected, non-parametric bootstrap replication with a minimum of 10,000 replications will be used to calculate confidence intervals and perform hypothesis testing.

With small samples, the normality of parameters, such as the sample mean, cannot be assured. Therefore, quantile-based confidence intervals will be obtained, and hypothesis testing will be conducted using comparisons of observed test statistics to test statistics obtained under the null hypothesis. For hypotheses of equivalence between two populations (e.g. placebo and dosage groups, $\beta_1 = 0, \mu_1 = \mu_2$), an unequal sample unequal variance T-statistic will be used:

$$T = \frac{\widehat{\mu}_1 - \widehat{\mu}_2}{s_p \sqrt{\frac{1}{n_1} + \frac{1}{n_2}}} \quad (1)$$

where, $\widehat{\mu}_1$ and $\widehat{\mu}_2$ are the observed sample means, and

$$s_p = \sqrt{\frac{(n_1-1)s_1^2 + (n_2-1)s_2^2}{n_1+n_2-2}} \quad (2)$$

Where s_1^2 and s_2^2 are the sample variances. The null distribution will be generated by resampling from the values at their two groups shifted to their pooled sample mean.

For joint significance tests (e.g. $H_0: \beta_1 = \beta_2 = \beta_3 = \beta_4 = 0$), the F-statistic will be used with the formula,

$$F_b = \frac{\left(\frac{RSS_1 - RSS_2}{p_2 - p_1}\right)}{\left(\frac{RSS_2}{n - p_2}\right)} \quad (3)$$

where RSS_1 is the residual sum of squares for an ANOVA model fit under the null with p_1 parameters and RSS_2 a model fit with all parameters p_2 included. The null distribution will be generated through resampling from the distributions of each dosage cohort shifted to their common mean. With bootstrap resampling, p-values will be calculated by comparing observed values of the test statistic to the null distribution:

$$p = \frac{1}{B} \sum_{b=1}^B I(F_b \geq F_{obs} \text{ or } |T_b| \geq |T_{obs}|) \quad (4)$$

where B is the number of bootstrap samples taken.

ANOVA also assumes homogeneity of variance (i.e. homoskedasticity). Homogeneity of variance will be assessed. If variances are equal, homogenous variance ANOVA will be

performed, otherwise heterogeneous variance ANOVA will be performed, unless bootstrapping is used.

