12.1.1. Pharmacokinetic Analysis

The PK analysis will be performed on the pharmacokinetics analysis set. Blood samples will be obtained for PK assessments prior to dosing and at 2, 5, 10, 15, 20, and 30 minutes and 1, 2, 4, 8, 12, 24, 36, and 48 hours post dose. Scopolamine HBT PK assessments will include

determination of the following parameters: observed C_{max} , T_{max} , V_d , $t_{1/2}$, Cl , AUC_{last} , AUC_{∞} , $C_{max}/Dose$, MRT, and $AUC_{\infty}/Dose$. Plasma concentration time profiles for each subject tested will be evaluated using semi-log plots and characterized using noncompartmental analysis (WinNonlin). PK data will also be summarized graphically by dose group. PK and safety endpoints will undergo PD analysis and evaluation.

Data for PK parameters will be summarized by group using descriptive statistics including mean, standard deviation, minimum, maximum, and may include median and quartiles. All PK data for individual participants will be provided in listings.

Dose proportionality will be tested for $C_{max}/Dose$ and $AUC_{\infty}/Dose$ using ANOVA models. Likelihood ratio tests will be used to test the joint hypothesis of equivalence across dose levels. Equivalence will be tested for each dose level against the next higher dose level. Equivalence of parameters across doses (dose equivalence) will be tested for T_{max} , $t_{1/2}$, V_d , and MRT. All ANOVA models of PK parameters will adjust for sex.

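### SAP 6.10 labels its two-group bootstrap statistic unequal-variance but prints the pooled formula, leaves the resampling scheme unclear, and gives no sex-adjusted version for the adjacent-dose PK tests (fallback branch only)

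*SAP*

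**What the plan says.** SAP 6.10 sets out a sequence for the ANOVA models. Residuals are checked for normality. Next, "If the normality assumption is not met, logarithmic (natural or base-10) transformation will be assessed". Finally, "If lognormality is rejected, non-parametric bootstrap replication with a minimum of 10,000 replications will be used".

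In that last branch, a comparison of two populations is to be made as follows: "an unequal sample unequal variance T-statistic will be used". Eq. 1 divides the difference in means by s_p·√(1/n1 + 1/n2), and Eq. 2 defines s_p as the pooled standard deviation. The numerator terms "are the observed sample means", with no covariate. The reference distribution is described in one sentence: "The null distribution will be generated by resampling from the values at their two groups shifted to their pooled sample mean". On unequal variances, the same section says "otherwise heterogeneous variance ANOVA will be performed, unless bootstrapping is used".

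On sex, protocol 12.1.1 states: "All ANOVA models of PK parameters will adjust for sex". SAP 4.4 repeats the requirement for PK analyses, and Eq. 8 in SAP 6.15.1 carries a sex term. Adjacent doses are compared by Wald tests of that model's parameters. SAP 6.15.1 mentions bootstrapping only for the joint test, through the F-statistic of Eq. 3. Protocol 12.5 describes a different fallback, in which the bootstrap supplies standard errors for model coefficients.

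**The concern.** There are three gaps in one fallback branch.

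1. **Label against formula.** A programmer cannot follow both the words and Eq. 1-2. Heterogeneous-variance ANOVA is switched off once bootstrapping is used, so Eq. 1 is where a two-group bootstrap test would have to deal with unequal variances.
2. **Resampling scheme.** The sentence on the null distribution does not make clear whether each group is resampled from its own shifted values or both are drawn from the combined shifted values. Only the first preserves the difference in variance under the null.
3. **Sex.** Eq. 3 is built from nested ANOVA fits, so the joint PK test can keep sex. The only two-group statistic printed is Eq. 1, which cannot. If it is used for adjacent doses, a difference in sex mix between cohorts enters the dose contrast.

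At stake are the error rate of dose-against-placebo safety tests and the validity of the adjacent-dose proportionality tests, in both cases only if this branch is reached.

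**Working it through.** **Inputs from the documents.** Active n per dose is 6 to 9 and pooled placebo n is 10 to 15 (SAP 3.4; pooling in SAP 6.3). Adjacent-dose tests number 4 per parameter × 2 parameters = 8 of 110 (SAP Table 7). They are two-sided, at alpha 0.05 alongside Benjamini-Hochberg. At least 1 man and 1 woman per dose receive active drug (SAP 3.4), so the split among 6 actives can run from 1:5 to 5:1. The documents attach no error rate to this method, so there is no planned figure to reproduce.

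**Assumptions.** SD ratio 2 or 3, sex difference 25%, CV 30%. The documents give none of these.

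**Step 1: which statistic is printed?** Coded as written, Eq. 1-2 equalled Student's t to four decimals in all seven configurations tried. They differed from Welch whenever n1 ≠ n2 (one 6 v 10 data set: 0.3266 against 0.2751). With n1 = n2 = 6, the squared denominator is (s1² + s2²)/2 × 2/6 = (s1² + s2²)/6, which is exactly the Welch value.

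For 6 v 10 with SD 2:1:
- Eq. 1-2: √[(5×4 + 9×1)/14 × (1/6 + 1/10)] = √0.552 = 0.743
- Welch: √(4/6 + 1/10) = √0.767 = 0.876
- ratio 0.743/0.876 = 0.85

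**Step 2: type I error.** Normal data, two-sided 5%, 2,000 data sets with 999 bootstrap draws each:

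| n1 v n2 | SD ratio | SE ratio, Eq. 1-2 / Welch | Eq. 1-2 within / combined | Welch within / combined |
|---|---|---|---|---|
| 6 v 6 | 2:1 | 1.00 | 3.8% / 5.5% | 3.8% / 5.5% |
| 6 v 9 | 2:1 | 0.88 | 5.6% / 9.6% | 4.4% / 6.6% |
| 6 v 10 | 2:1 | 0.85 | 5.4% / 9.9% | 4.4% / 6.2% |
| 6 v 15 | 2:1 | 0.75 | 6.6% / 12.4% | 3.8% / 5.8% |
| 6 v 15 | 3:1 | 0.68 | 6.6% / 17.8% | 3.6% / 7.5% |
| 6 v 10 | 1:2 | 1.17 | 4.2% / 3.1% | 4.6% / 5.0% |

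Across all runs with the larger SD in the smaller group, the ranges are about 5-7% / 9-19% for Eq. 1-2 and 3-5% / 6-8% for Welch. With the larger SD in the larger group, Eq. 1-2 is conservative.

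A cohort with 6 actives contributes only 2 placebos, so its pooled placebo group cannot exceed 2 + 4×3 = 14. The 6 v 15 rows are therefore one participant beyond the design. At 6 v 14 and SD 3:1 the SE ratio is √[(5×9 + 13)/18 × (1/6 + 1/14)] / √(9/6 + 1/14) = 0.876/1.254 = 0.70, and the simulated errors stay inside the same ranges.

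**Step 3: sex in the adjacent-dose contrast.** The bias on the log scale is the difference in female fraction × ln 1.25 (0.223).
- 2:4 v 4:2: (4 − 2)/6 × 0.223 = 0.074, ratio 1.077, a false difference of about 8%.
- 1:5 v 5:1: (5 − 1)/6 × 0.223 = 0.149, ratio 1.160, about 16%.

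With Eq. 1-2, within-group bootstrap, 6 v 6 and lognormal values at CV 30%, rejection is about 3% in the first case (2.8% and 3.4% in two runs) and 7-8% in the second (6.9% and 7.8%). Rejection stays below 5% in the first case because the ignored sex difference also inflates the within-group SD. In a separate normal-data simulation at 6 v 6, with sex effects of 0.5 to 1.5 SD, a sex-adjusted linear model held 4-6% in every scenario.

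**Step 4: how likely is the imbalance?** In a cohort of 4 men and 4 women with 2 placebos, a 2:4 or 4:2 active split has probability 12/28 = 43%. The pairing 1:5 v 5:1 needs adjacent cohorts at opposite sex limits and both placebos in the minority sex each time. Even given those compositions, the chance is (3/28)² ≈ 1.1%.

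**The case against.** **The loss of sex adjustment is inferred.** A reader might conclude that the SAP orders unadjusted PK contrasts. It does not. Eq. 1 is illustrated with placebo against dosage groups, and placebo is excluded from PK. SAP 4.4 and 6.15.1 require sex adjustment without a bootstrap exception, and protocol 12.5 would keep sex by bootstrapping model coefficients. This stands: the defect is that the branch does not say how sex is carried for 8 of 110 tests, and the only two-group statistic it prints cannot carry it.

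**The pooled formula does little harm under a bootstrap.** This is correct for within-group draws, where Eq. 1-2 is often as close to 5% as Welch. It is not correct if the shifted groups are combined, and the text does not rule that out.

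**Larger error rates might be inferred** by referring Eq. 1-2 to t tables, or by testing sex imbalance with a Welch test on log values. Neither is this branch: Eq. 4 uses the bootstrap null, and the branch is entered only after lognormality fails. Nor should the sex bias be compared with the size of the dose steps, because the parameters are dose-normalised and equal under proportionality.

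**The log step** cannot be applied to BPRS and DSST change scores at or below zero, or to VAS scores of zero. The transformation is only to be assessed, and the next step is the bootstrap in any case, so this is a minor wording matter.

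**Conclusion.** The mismatch between label and formula is certain from the page. It concerns a fallback only, so the primary analyses are untouched, and it has no effect at 6 v 6. It matters for dose against pooled placebo and for 6 v 9 comparisons between an unexpanded and an expanded cohort. The resampling sentence drives the size: modest error if draws are within group, roughly two to four times nominal if combined, under assumed SD ratios of 2-3 with the larger SD in the smaller group. The simulations are two-sided, as Eq. 4 is printed; SAP 6.3 makes the safety tests one-sided, so the figures are a guide there.

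The missing sex-adjusted bootstrap is a gap against the SAP's own requirement. At a plausible imbalance it biases the contrast by about 8% without raising the rejection rate. The 16% bias and 7-8% rejection belong to an extreme and unlikely case. Both rest on an assumed 25% sex difference and 30% CV. Severity: minor.

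**What to change.** In SAP 6.10:
- Replace the Eq. 1-2 denominator by √(s1²/n1 + s2²/n2), so that the formula matches the label.
- State that each group is resampled from its own values after shifting to the common mean.
- For the 8 adjacent-dose PK contrasts, bootstrap residuals within dose from the sex-adjusted Eq. 8 model and use that model's contrast t-statistic. This agrees with protocol 12.1.1 and stays close to protocol 12.5.
- Optionally, add that the log step is skipped for change scores and VAS.

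The cost is a few lines of SAP text and code in a fallback branch, to be settled before unblinding. Nothing in the conduct of the trial or in data collection changes.
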